#### Table 6a Adverse events

	Adverse event, n (%)		p-value
	AL	AL Multivitamin	
	(N=XXX)	(N=XXX)	
Signs and symptoms			
Headache	XX (XX.X)	XX (XX.X)	0.XXX
Loss of appetite	XX (XX.X)	XX (XX.X)	0.XXX
Dizziness	XX (XX.X)	XX (XX.X)	0.XXX
Fatigue	XX (XX.X)	XX (XX.X)	0.XXX
Joint pain	XX (XX.X)	XX (XX.X)	0.XXX
Muscle pain	XX (XX.X)	XX (XX.X)	0.XXX
Abdominal pain	XX (XX.X)	XX (XX.X)	0.XXX
Nausea	XX (XX.X)	XX (XX.X)	0.XXX
Vomiting	XX (XX.X)	XX (XX.X)	0.XXX
Diarrhoea	XX (XX.X)	XX (XX.X)	0.XXX
Itching	XX (XX.X)	XX (XX.X)	0.XXX

Cough	XX (XX.X)	XX (XX.X)	0.XXX
Fever	XX (XX.X)	XX (XX.X)	0.XXX
Serious adverse events	XX (XX.X)	XX (XX.X)	0.XXX

#### Table 6b Adverse events by severity

		AL					Multivitamin					
	Highest grade					Highest grade						
		Modera		Life-			Modera		Life-			
AE, n (%)	Mild	te	Severe	threatening	Fatal	Mild	te	Severe	threatening	Fatal		
	XX	XX	XX	XX (XX.X)	XX	XX	XX	XX	XX (XX.X)	XX		
Headache	(XX.X)	(XX.X)	(XX.X)		(XX.X)	(XX.X)	(XX.X)	(XX.X)		(XX.X)		
Loss of	XX	XX	XX	XX (XX.X)	XX	XX	XX	XX	XX (XX.X)	XX		
appetite	(XX.X)	(XX.X)	(XX.X)		(XX.X)	(XX.X)	(XX.X)	(XX.X)		(XX.X)		
	XX	XX	XX	XX (XX.X)	XX	XX	XX	XX	XX (XX.X)	XX		
Dizziness	(XX.X)	(XX.X)	(XX.X)		(XX.X)	(XX.X)	(XX.X)	(XX.X)		(XX.X)		
	XX	XX	XX	XX (XX.X)	XX	XX	XX	XX	XX (XX.X)	XX		
Fatigue	(XX.X)	(XX.X)	(XX.X)		(XX.X)	(XX.X)	(XX.X)	(XX.X)		(XX.X)		
	XX	XX	XX	XX (XX.X)	XX	XX	XX	XX	XX (XX.X)	XX		
Joint pain	(XX.X)	(XX.X)	(XX.X)		(XX.X)	(XX.X)	(XX.X)	(XX.X)		(XX.X)		
	XX	XX	XX	XX (XX.X)	XX	XX	XX	XX	XX (XX.X)	XX		
Muscle pain	(XX.X)	(XX.X)	(XX.X)		(XX.X)	(XX.X)	(XX.X)	(XX.X)		(XX.X)		
Abdominal	XX	XX	XX	XX (XX.X)	XX	XX	XX	XX	XX (XX.X)	XX		
pain	(XX.X)	(XX.X)	(XX.X)		(XX.X)	(XX.X)	(XX.X)	(XX.X)		(XX.X)		
	XX	XX	XX	XX (XX.X)	XX	XX	XX	XX	XX (XX.X)	XX		
Nausea	(XX.X)	(XX.X)	(XX.X)		(XX.X)	(XX.X)	(XX.X)	(XX.X)		(XX.X)		
	XX	XX	XX	XX (XX.X)	XX	XX	XX	XX	XX (XX.X)	XX		
Vomiting	(XX.X)	(XX.X)	(XX.X)		(XX.X)	(XX.X)	(XX.X)	(XX.X)		(XX.X)		
	XX	XX	XX	XX (XX.X)	XX	XX	XX	XX	XX (XX.X)	XX		
Diarrhoea	(XX.X)	(XX.X)	(XX.X)		(XX.X)	(XX.X)	(XX.X)	(XX.X)		(XX.X)		
	XX	XX	XX	XX (XX.X)	XX	XX	XX	XX	XX (XX.X)	XX		
Itching	(XX.X)	(XX.X)	(XX.X)		(XX.X)	(XX.X)	(XX.X)	(XX.X)		(XX.X)		
	XX	XX	XX	XX (XX.X)	XX	XX	XX	XX	XX (XX.X)	XX		
Cough	(XX.X)	(XX.X)	(XX.X)		(XX.X)	(XX.X)	(XX.X)	(XX.X)		(XX.X)		
	XX	XX	XX	XX (XX.X)	XX	XX	XX	XX	XX (XX.X)	XX		
Fever	(XX.X)	(XX.X)	(XX.X)		(XX.X)	(XX.X)	(XX.X)	(XX.X)		(XX.X)		

### Table 6c Adverse events by relationship to study drug

		AL				Multivitamin			
		Relationsh	nip to drug		Relationship to drug				
AE, n (%)	Unrelated	Probably	Possibly	Definitely	Unrelated	Probably	Possibly	Definitely	
Headache	XX (XX.X)	XX (XX.X)	XX (XX.X)	XX (XX.X)	XX (XX.X)	XX (XX.X)	XX (XX.X)	XX (XX.X)	
Loss of appetite	XX (XX.X)	XX (XX.X)	XX (XX.X)	XX (XX.X)	XX (XX.X)	XX (XX.X)	XX (XX.X)	XX (XX.X)	
Dizziness	XX (XX.X)	XX (XX.X)	XX (XX.X)	XX (XX.X)	XX (XX.X)	XX (XX.X)	XX (XX.X)	XX (XX.X)	
Fatigue	XX (XX.X)	XX (XX.X)	XX (XX.X)	XX (XX.X)	XX (XX.X)	XX (XX.X)	XX (XX.X)	XX (XX.X)	
Joint pain	XX (XX.X)	XX (XX.X)	XX (XX.X)	XX (XX.X)	XX (XX.X)	XX (XX.X)	XX (XX.X)	XX (XX.X)	

| Muscle pain    | XX (XX.X) |
|----------------|-----------|-----------|-----------|-----------|-----------|-----------|-----------|-----------|
| Abdominal pain | XX (XX.X) |
| Nausea         | XX (XX.X) |
| Vomiting       | XX (XX.X) |
| Diarrhoea      | XX (XX.X) |
| Itching        | XX (XX.X) |
| Cough          | XX (XX.X) |
| Fever          | XX (XX.X) |

# 4.4.6 Prevalence of asymptomatic Plasmodium infections in high risk populations at varying seasonal time points

Prevalence of asymptomatic Plasmodium at baseline, stratified by season and risk factors will be presented in table 7 below. The numbers of asymptomatic Plasmodium infections will be visuallized by follow-up months and study arm in figure 2 below.

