6.3. Randomisation and blinding

Participants who fulfil all the inclusion criteria and have none of the exclusion criteria will be randomised 1:1 to one of the two treatment arms according to a randomisation schedule. Randomisation will be in blocks of size that will be determined by the trial statistician and the block

size will not be revealed to the investigating team. Allocation will be done by drawing the next sequential numbered opaque envelope (or other equally reliable randomisation administration procedure), which contains the study number and treatment allocation.

The participants will be assigned a study arm through a computer-generated randomisation schedule. Individual, sealed and sequentially numbered envelopes will be provided for each trial site with one envelope per participant, indicating the treatment allocation.

This is an open-label study so the blinding of investigators and participants is not applicable. However, the randomisation procedure allows for adequate drug allocation concealment before envelopes are opened. All laboratory investigations will be performed without knowledge of the treatment allocation.

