6.6. Follow-up

Participants will be asked to return for a follow-up assessment any time from 28 to 35 days after commencing prophylaxis. This will be regardless of the duration of their visit to the forest or the number of times they visited it in that period. At this assessment, they will be interviewed about how long they spent in the forest, where they went, why, who they travelled with and about risk factors for infection. Brief physical examinations, vital sign and symptom questionnaire will be performed. They will also be asked to report any diagnostic tests and/or treatment for malaria during the preceding 28-35 days.

Blood sampling at follow-up

At each follow-up visit, the following blood will be taken:

All individuals:

- Parasite PCR (Up to 1 ml).

- Dried blood spot for lumefantrine level (0.2 ml)

In those with confirmed clinical malaria at any time point between enrolment and follow-up:

- Dry blood blots (0.4 ml, 3 spots) collected on filter papers for:
 - o Parasite DNA genotyping for genetic markers of antimalarial resistance.
 - o Parasite whole genome sequencing and barcoding to identify geographical origin of parasites and compare genotypes to identify persistent infections.

In individuals who are planning to return again to the forest within the following 28 days after the follow up visit, they will be asked to continue their weekly prophylaxis according to the original treatment allocation on enrolment. They will then be asked to return for a second follow-up visit a further 28 to 35 days later when the above procedure will be repeated. This will be repeated one more time. If the person cannot be followed up within the scheduled period, e.g. because they do not return from the forest in time, then they will be followed up at the first opportunity and this will be recorded in the CRF.

Thus individuals may take prophylaxis continuously for a maximum of 3 periods of 28-35 days in the forest plus 4 weeks after returning totaling 112 days. The choice of study medication for each individual will follow the initial assignment on enrolment throughout the follow-up period.

In those who do not declare an intention to return to the forest within 28 days at any follow-up visit, no further follow-up visits will be offered at that time but they will be asked to complete 4 weeks of prophylaxis following their last day in the forest as post-exposure prophylaxis.

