9 STATISTICAL CONSIDERATIONS

9.1 Sample size justification

The target population for this study will be adult Cambodians who work and sleep in the forest (farmers, collect forest goods, hunting, etc.). 2,200 study participant episodes are required in each arm to have sufficient power to detect a statistically significant difference between the treatment arm and a control arm. The estimate of the required sample size is complicated by the scarce data on *P. falciparum* incidence in forest workers. We estimate the required sample size based on our study in forest rangers in Vietnam in 2016 (13) combined with an estimate of the time spent in the forest from ongoing studies in northeast Cambodia. In Viet Nam, we found that 1 forest ranger became infected per 500 person-nights spent in the forest. We estimate conservatively that during each episode, each participant will spend at least 10 days in a high-risk zone. We will need 20 infectious bites per study-arm: $2 \times 20 = 40$ (i.e. irrespective of protection afforded per arm). Risk days/nights needed: $40 \times 500 = 20,000$. Each participant episode contributes 10 risk days/nights: $20,000/10 = 2,000$ episodes required. The assumed loss to follow-up could be as high as 10% =200. Therefore, the total sample required is $2,000+200=2,200$ study participant episodes.

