- Detailed data and GPS mapping on a subset of participants and their peers relating to the behaviours and risk factors associated with malaria infection

- To determine the prevalence of asymptomatic Plasmodium infections in high risk populations at varying seasonal time points.
   Endpoint
  - Overall prevalence of Plasmodium at baseline, stratified by season and risk factors
- 2.4 GENERAL

The study takes place at up to 50 villages in selected malaria endemic districts in Stung Treng and Pursat Provinces, Cambodia. As the malaria situation in these areas is dynamic, the villages will be identified prior to the start of the trial from analysis of up to date malaria incidence from passive surveillance collected by the Cambodia National Center for Parasitology Entomology and Malaria Control. If there are found to be insufficient villages with malaria cases in Stung Treng Province at the time of trial commencement, we will include additional sites in Pursat Province. MORU has existing study sites and teams in both provinces which will support the running of this trial. The rationale for choosing these areas include high forest cover and ongoing malaria transmission among forest goers.

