#### 2.5 DETERMINATION OF SAMPLE SIZE

The target population for this study will be adult Cambodians who work and sleep in the forest (farmers, collect forest goods, hunting, etc.). 2,200 study participant episodes are required in each arm to have sufficient power to detect a statistically significant difference between the treatment arm and a control arm. The estimate of the required sample size is complicated by the scarce data on *P.falciparum* (*Pf*) incidence in forest workers. Formally, we anticipate that the risk of being Pf positive without receiving prophylaxis will be around 5%. A total of 1,605 participant-episodes per arm are enough to detect a difference of at least 40% in the proportion of episodes with a Pf positive result as defined by the 28-day PCR parasite positivity rate i.e. from 5% positivity in participants without receiving antimalarial prophylaxis (i.e. multivitamin) to 3% positivity in participants receiving artemether-lumefantrine prophylaxis. This has been estimated with 80% power and 5% significance level. However, we also anticipate that we will likely observe multiple episodes being recruited into the study that can reduce power of the study if not accounted for. To compensate for the multiple episodes and any losses to follow up, we plan to recruit approximately 600 (i.e. 595) additional episodes in each group on top of the required 1605 single episodes. This gives an additional 27% episodes to account for the multiple episodes and losses to follow up. Thus, the overall sample size will be 4,400 episodes (i.e. 2,200 episodes in the treatment arm and 2,200 episodes in the control arm). The sample size calculations have been performed in Stata version 15.

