#### Table 7 Prevalence of asymptomatic Plasmodium infection at baseline

	Prevalence of asymptomatic Plasmodium infection at baseline, n (%)					
	AL	Multivitamin	Total			
	(N=XXX)	(N=XXX)				
Overall	XX (XX.X)	XX (XX.X)	XX (XX.X)			
Season						
Month 1	XX (XX.X)	XX (XX.X)	XX (XX.X)			
Month 2	XX (XX.X)	XX (XX.X)	XX (XX.X)			
Month 3	XX (XX.X)	XX (XX.X)	XX (XX.X)			
Riskfactor1						
Category1	XX (XX.X)	XX (XX.X)	XX (XX.X)			
Category2	XX (XX.X)	XX (XX.X)	XX (XX.X)			
Riskfactor2						
Category1	XX (XX.X)	XX (XX.X)	XX (XX.X)			
Category2	XX (XX.X)	XX (XX.X)	XX (XX.X)			
Riskfactor3						
Category1	XX (XX.X)	XX (XX.X)	XX (XX.X)			
Category2	XX (XX.X)	XX (XX.X)	XX (XX.X)			

[figure not shown]

Figure 2 Number of asymptomatic Plasmodium cases by follow-up months

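### Figure 2 is defined as a count of asymptomatic infections by follow-up month and arm with no stated number tested, so it will tend to fall as fewer people are followed even if prevalence is constant

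*SAP*

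**What the plan says.** SAP 4.4.6 addresses the secondary objective listed in SAP 2.3: "To determine the prevalence of asymptomatic Plasmodium infections in high risk populations at varying seasonal time points". It plans two outputs. Table 7 gives baseline prevalence as n (%), by arm and in total, split by season and risk factor. The second output is a figure: "The numbers of asymptomatic Plasmodium infections will be visuallized by follow-up months and study arm in figure 2 below". Its caption reads "Figure 2 Number of asymptomatic Plasmodium cases by follow-up months". The text and the caption therefore agree on a count, and neither mentions a percentage or a denominator.

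Protocol 6.6 decides who can contribute to each month. A second visit is requested only for a subgroup: "In individuals who are planning to return again to the forest within the following 28 days after the follow up visit". The same rule applies once more for the third visit. For everyone else, "no further follow-up visits will be offered at that time".

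**The concern.** An expected count is the number tested multiplied by the prevalence. When the number tested changes from month to month, a plot of counts mixes infection with continued follow-up. Here the number scheduled for testing can only stay level or fall within an enrolment, because each later visit depends on a declared plan to return to the forest. Re-enrolment under Protocol 6.6 does not offset this, since each new enrolment starts again at a Month 1 visit.

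A reader of Figure 2 could take a fall from Month 1 to Month 3 as falling infection when fewer people were tested. If the two arms also had different numbers tested, part of any gap between them would reflect that difference. Planning a further trip and attending a visit both happen after randomisation, in a trial where "This is an open-label study so the blinding of investigators and participants is not applicable", so randomisation does not guarantee equal numbers at later visits.

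**Working it through.** **Inputs from the documents**
- Recruited: 2,200 episodes per arm (Protocol 9.1, SAP 2.5).
- Loss to follow-up: "The assumed loss to follow-up could be as high as 10% =200" (Protocol 9.1).
- Positivity: 5% on multivitamin, "to 3% positivity in participants receiving artemether-lumefantrine prophylaxis" (SAP 2.5). These are *P. falciparum* 28-day PCR rates, borrowed here as a plausible scale for asymptomatic infection.

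**Inputs assumed**
- The 10% loss is applied to the 2,200 recruited: 2,200 × 0.90 = 1,980 tested per arm at Month 1.
- Month-to-month retention *r* is not in the documents, so 90%, 70% and 50% are shown.

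**The plan's own figure.** With 5% v 3%, 80% power and a two-sided 5% level, the usual two-proportion formula gives 1,506 per arm. Adding the continuity correction gives 1,605, the stated figure. This confirms how the 5% and 3% rates were used; the point itself does not depend on it.

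**Counts at constant prevalence.** Expected count at Month *k* = 1,980 × *r*^(*k*−1) × 0.05.

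| Retention | Tested, Months 1/2/3 | Expected count, Months 1/2/3 | Apparent fall by Month 3 (1 − *r*²) |
|---|---|---|---|
| 90% | 1,980 / 1,782 / 1,604 | 99 / 89 / 80 | 19% |
| 70% | 1,980 / 1,386 / 970 | 99 / 69 / 49 | 51% |
| 50% | 1,980 / 990 / 495 | 99 / 50 / 25 | 75% |

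The apparent fall does not depend on the prevalence chosen, because 0.05 cancels. Plotted as n/N, every row is flat at 5%.

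**Arm comparison, only if the numbers tested differ.** At equal 5% prevalence the ratio of counts equals the ratio of the proportions tested.
- 90% v 80% of 2,200 tested: 99 v 88, ratio 0.89.
- 90% v 70%: 99 v 77, ratio 0.78.
- To imitate the whole planned effect (3%/5% = 0.60) would take 90% v 54%, since 0.54/0.90 = 0.60.
- The distortion can also hide a benefit. AL at 3% with 90% tested gives 2,200 × 0.90 × 0.03 = 59.4; multivitamin at 5% with 54% tested gives 2,200 × 0.54 × 0.05 = 59.4.

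**Whether other outputs supply the denominator.** Table 2 (SAP 4.3.2) and Table 3 (SAP 4.4.1) give n (%) by month and arm, but for PCR positivity or clinical malaria combined, and their layout carries one N per arm rather than one per month. The trial profile in SAP 4.1 promises only the number assessed for the 28-day endpoint. No month-specific number tested is promised in the text.

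**The case against.** Several points on the other side stand.

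- **The image is missing.** The available text does not show Figure 2, so percentages or numbers tested may be printed on the mock-up. What can be said is that neither the text nor the caption promises them.
- **The prevalence endpoint is not reported as counts.** A reader might infer that it is. Protocol 5.4.2 and SAP 2.3 define that endpoint at baseline, and Table 7 reports it as n (%). Figure 2 is an addition.
- **Infection over time is not left to this figure alone.** Tables 2 and 3 give percentages by month and arm, with a risk difference or incidence rate ratio, 95% CI and p-value. They use the composite outcome, so they are not a full substitute, but they limit the scope for misreading.
- **A steep fall is not certain.** At 90% retention it is 19%. The direction follows from the follow-up rule; the size cannot be known from the documents.
- **An arm artefact is not shown.** A reader might infer that Figure 2 will create or hide a treatment effect. Nothing in the documents indicates different attendance by arm. Even 99 v 77 is a difference of 22 against a Poisson standard error of √(99 + 77) = 13.3, so it is within ordinary chance variation (22/13.3 = 1.7).

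None of this answers the central point. As defined, the figure shows counts over a number tested that shrinks by design, and no planned output gives the matching denominator.

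**Conclusion.** The point holds as a minor one. Following the stated definition, Figure 2 will tend to decline from Month 1 to Month 3 at constant prevalence, by 19% to 75% for retention between 90% and 50%. The assumptions are 1,980 tested per arm at Month 1, the same retention at each step, and retention values that are illustrative because the documents give none. Distortion between arms is conditional on unequal numbers tested and should be described only as possible. The figure is descriptive, carries no test and serves a secondary objective, so the primary estimate and its test are untouched.

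**What to change.** In SAP 4.4.6 and the Figure 2 caption, replace the number of infections with the proportion positive (n/N tested) by follow-up month and arm, with a 95% CI, and print N tested under each bar. Where a person contributes more than one episode to the same month through re-enrolment, the robust standard error already specified in SAP 4.3 can be used for the interval.

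Add one sentence to the caption saying that those tested at Months 2 and 3 are a selected group planning to return to the forest. Proportions remove the denominator artefact but not this selection, so differences between months should not be read as change within one fixed population.

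The cost is one figure definition and its caption. PCR is already scheduled at every follow-up visit (Protocol 6.6 and Appendix 1), so no new data are needed.

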#### Table 7 Prevalence of asymptomatic Plasmodium infection at baseline

	Prevalence of asymptomatic Plasmodium infection at baseline, n (%)					
	AL	Multivitamin	Total			
	(N=XXX)	(N=XXX)				
Overall	XX (XX.X)	XX (XX.X)	XX (XX.X)			
Season						
Month 1	XX (XX.X)	XX (XX.X)	XX (XX.X)			
Month 2	XX (XX.X)	XX (XX.X)	XX (XX.X)			
Month 3	XX (XX.X)	XX (XX.X)	XX (XX.X)			
Riskfactor1						
Category1	XX (XX.X)	XX (XX.X)	XX (XX.X)			
Category2	XX (XX.X)	XX (XX.X)	XX (XX.X)			
Riskfactor2						
Category1	XX (XX.X)	XX (XX.X)	XX (XX.X)			
Category2	XX (XX.X)	XX (XX.X)	XX (XX.X)			
Riskfactor3						
Category1	XX (XX.X)	XX (XX.X)	XX (XX.X)			
Category2	XX (XX.X)	XX (XX.X)	XX (XX.X)			

[figure not shown]

Figure 2 Number of asymptomatic Plasmodium cases by follow-up months
